## **6.5. Study Drug Compliance**

For subjects in the safety population, overall compliance (%) for INCB059872 will be calculated for all subjects as

$$\text{compliance (\%)} = 100 \times [\text{total dose actually taken}] / [\text{total prescribed dose}].$$

The total prescribed dose is defined as the sum of the doses prescribed by the investigator accounting for dose modifications.

The total actual dose taken will be calculated based on information entered on the drug accountability eCRF. If there are dispensed drugs that have not been returned yet, the actual dose taken starting from the dispense date of the unreturned drugs will be imputed by the dose taken as reported on the dosing eCRF.

## **6.6. Prior and Concomitant Medication**

Prior medications and concomitant medications will be coded using the WHO Drug Dictionary. Number and percentage of subjects in the FAS with each prior and concomitant medications will be summarized by WHO drug class and WHO drug preferred term.

## 7. EFFICACY

[Appendix A](#) provides a list of data displays. Sample data displays are included in a separate document.

### 7.1. General Considerations

For subjects with solid tumors, AML, and MDS, the proportion of subjects who meet the response criteria as appropriate for the tumor type will be summarized with descriptive statistics.

For MF subjects, changes and percentage changes in spleen volume from baseline to Week 12 [REDACTED] will be summarized descriptively. All efficacy analyses will be performed using the FAS.

### 7.2. Efficacy Hypotheses

Not applicable.

### 7.3. Analysis of the Efficacy Parameters

#### 7.3.1. Solid Tumors

##### 7.3.1.1. Response Assessment

Tumor assessment for subjects with solid tumors will be performed using RECIST v1.1 ([Eisenhauer et al 2009](#)). The investigator's assessment will be used to determine responses and will be logged into the eCRF. The schedule for solid tumor assessment will be at screening, every 8 weeks during the study treatment, at the EOT visit, and every 8 to 9 weeks during the disease status follow-up.

Response status per investigator's assessment for solid tumor will be recorded at each response assessment visit as CR, PR, SD, PD, NE, or not assessed.

[figure not shown]
##### 7.3.1.2. Best Overall Response and Objective Response Rate

Best overall response for subjects with solid tumors is the best response recorded before and including the first PD, in the order of CR, PR, SD, PD, and NE. In the case of SD, measurements must meet the SD criterion at least once on or after Day 42. Subjects who fail to meet this criterion will have a BOR of PD if the next available assessment after the initial assessment indicates PD, or a BOR of NE if there are no additional assessments available.

[figure not shown]
A subject is considered a responder if the subject has a BOR of CR or PR.

Objective response rate is the proportion of responders. Subjects who do not have sufficient baseline or on-study response assessment information to be adequately assessed for response status will be included in the denominators in the calculations of ORR.

Best overall response will be summarized descriptively. Objective response rate will be estimated with its 95% CI. Confidence intervals will be calculated based on the exact method for binomial distributions.

CONFIDENTIAL

#### **7.3.1.6. Best Change in Target Lesion Size**

For subjects with measurable lesions at baseline, target lesion sizes will be measured by the sum of diameters. The best percentage change from baseline, defined as the largest decrease in target lesion sizes during the study, will be summarized and a waterfall plot of the best percentage change will be generated. Note that for subjects who only have increases in target lesion sizes from baseline, the smallest increase will be considered as the best change from baseline.

Per RECIST criteria, target lesions considered “too small to measure” will be assigned a default value of 5 mm for purposes of this analysis. Likewise, target lesions identified as “not present” at postbaseline assessments will be assigned 0 mm for this analysis. In the event that a target lesions is unaccounted for in a particular postbaseline timepoint (ie, the assessment is missing or NE), then the overall sum of target lesions will not be evaluable for that post baseline timepoint.

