## 5.5. Withdrawal of Subjects From Study Treatment

### 5.5.1. Withdrawal Criteria

Subjects **must** be withdrawn from study drug for the following reasons:

- The subject becomes pregnant.
- Consent is withdrawn. Note: Consent withdrawn means that the subject can no longer be followed. Subjects may choose to discontinue study treatment and remain in the study to be followed for disease progression.
- Further participation would be injurious to the subject's health or well-being, in the investigator's medical judgment.
- The study is terminated by the sponsor.
- The study is terminated by the local health authority, IRB, or IEC.
- Unacceptable toxicity has occurred.
- Disease progression has occurred, except in the circumstance where, in the setting of otherwise stable disease, a medical procedure or radiation therapy is required to a single lesion, with medical monitor approval.

A subject **may** be discontinued from study treatment as follows:

- If, during the course of the study, a subject is found not to have met eligibility criteria, the medical monitor, in collaboration with the investigator, will determine whether the subject should be withdrawn from the study.
- If a subject is noncompliant with study procedures or study drug administration in the investigator's opinion, the sponsor should be consulted for instruction on handling the subject.

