### **5.6.2. Prohibited Medications**

Subjects are prohibited from receiving the following therapies during the screening and treatment periods of this study:

- Use of any anticancer drugs during study.
- Hydroxyurea is prohibited within 48 hours before initiation of study treatment during the screening period and within 24 hours before collection of [REDACTED].
- Aspirin in doses exceeding 81 mg/day.
- Use of potent inhibitors of CYP2D6 or potent inhibitors or inducers of CYP3A4 ([Appendix B](#)).

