## **7.6. Efficacy Assessments**

Objective assessment of tumor status is required using appropriate disease-specific techniques, and the investigator's assessment will be used to determine responses and will be logged into the eCRF. For SCLC/solid tumors subjects, Response Evaluation Criteria in Solid Tumors (RECIST) v1.1 ([Eisenhauer et al 2009](#)) will be used, and the recommended method for measuring and following tumor burden will be CT scan or MRI, to include the thorax, abdomen, and pelvis; the neck can be included if needed. Alternative modalities may be substituted for a CT scan at the discretion of the investigator, provided that the same modality is used throughout the study and the methodology is consistent with RECIST v1.1.

For AML subjects, the International Working Group Response Criteria for Acute Myeloid Leukemia ([Cheson et al 2003](#), [Appendix D](#)) will be used as the recommended method for measuring and following disease status. For MDS subjects, International Working Group Response Criteria for MDS ([Cheson et al 2006](#), [Appendix F](#)) will be used as the recommended method for measuring and following disease status. For MF subjects, the proposed Response Criteria for MF ([Tefferi et al 2013](#), [Appendix G](#)) will be used as the recommended method for measuring and following disease status.

The schedule for disease assessments will be at screening (this will be considered the baseline assessment) for all subjects and then once every 8 weeks throughout the study for solid tumor and once every 4 weeks for AML/MDS. The schedule for MF disease assessments will be at screening (this will be considered the baseline assessment), once every 4 weeks until Week 24, and once every 12 weeks after Week 24. For subjects who discontinue treatment for reasons other than disease progression, every effort should be made to continue monitoring their disease

status until the start of new anticancer therapy, documented disease progression, death, or end of study, whichever occurs first.

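### Best change in target lesion size has no cut at local treatment or first PD, so permitted surgery or radiation to a target lesion can be displayed as shrinkage on INCB059872

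*SAP*

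**What the plan says.** Protocol 5.5.1 (Withdrawal Criteria) makes disease progression a reason for mandatory withdrawal from study drug. It makes one exception, for otherwise stable disease where "a medical procedure or radiation therapy is required to a single lesion, with medical monitor approval". The exception does not say whether the lesion may be a target lesion.

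A subject who stays on drug continues to be imaged, under Protocol 7.6, "once every 8 weeks throughout the study for solid tumor". Protocol 5.6.2 prohibits "Use of any anticancer drugs during study" and lists neither local procedures nor radiation.

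SAP 7.3.1.6 works on the sum of target lesion diameters. The best percentage change is "defined as the largest decrease in target lesion sizes during the study". Target lesions identified as absent "at postbaseline assessments will be assigned 0 mm for this analysis". A timepoint drops out only when a target lesion is missing or not evaluable: "then the overall sum of target lesions will not be evaluable for that post baseline timepoint". The results go to Table 2.3.4 and to the waterfall plot in Figure 4.3.4.

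Best overall response for the same subjects has a narrower window. Under SAP 7.3.1.2 it "is the best response recorded before and including the first PD".

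**The concern.** The Protocol creates a situation that the SAP does not handle. A target lesion can be removed or irradiated while the subject stays on drug, and later scans still count toward best change. The rule does not ask why a lesion is smaller or gone. A removed lesion recorded as absent enters as 0 mm. An irradiated lesion enters at its reduced size, at 5 mm if too small to measure, or at 0 mm if absent.

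Best change and the waterfall plot are the planned lesion-size displays for the solid-tumor groups (TG B, B1, B2, E and E1), and antitumor activity is a secondary objective. There is no control group against which such an artefact would show up. The two solid-tumor summaries also use different windows, and the SAP gives no reason.

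**Working it through.** The documents state no figure for best change, so there is nothing to reproduce. The check has three steps.

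**1. Trace one subject through the rules.**
- A target lesion is treated locally under the Protocol 5.5.1 exception and study drug continues.
- Scans continue every 8 weeks (Protocol 7.6).
- If the lesion is recorded as absent, it scores 0 mm (SAP 7.3.1.6). The sum is evaluable and counts.
- If the site records the lesion as not evaluable, the sum is not evaluable and does not count. No readable text tells the site to do this.
- If PD was recorded before the local treatment, best overall response has already stopped (SAP 7.3.1.2). Best change has not.

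**2. Direction.** Best change is the minimum, over evaluable timepoints, of the percentage change from baseline. Adding post-treatment timepoints to that set can lower the minimum or leave it alone. It cannot raise it.

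**3. Size, as an illustration.** Assume k equal-sized target lesions, of which one is removed and scored 0 mm. The lesions have changed by a proportion g from baseline, and the untreated ones stay at that size.

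Percentage change under the SAP rule = 100 × [(k − 1)(1 + g)/k − 1]

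For example, k = 2 and g = 0 gives 100 × (1/2 − 1) = −50%. With k = 3 and g = 0.10 it gives 100 × (2 × 1.10/3 − 1) = −26.7%.

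| g | Change before local treatment | k = 1 | k = 2 | k = 3 | k = 4 | k = 5 |
|---|---|---|---|---|---|---|
| 0% | 0% | −100% | −50% | −33.3% | −25% | −20% |
| 10% | +10% | −100% | −45% | −26.7% | −17.5% | −12% |
| 20% | +20% | −100% | −40% | −20% | −10% | −4% |

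In every cell the rule reports a decrease although the lesions were stable or growing. If only scans before the local treatment are used, the result is the second column whatever the value of k. For unequal lesions with the rest stable, the spurious decrease equals the treated lesion's share of the baseline sum.

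The values of k and g and the equal sizes are assumptions; the documents give none of them.

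**The case against.** **The case is narrow.** The exception covers a single lesion, in otherwise stable disease, with medical monitor approval. Other subjects must stop drug at progression. Disease-status follow-up covers only those who stopped for another reason, and it ends at progression or new antineoplastic therapy (Protocol 6.4.2). Few planned scans after PD exist outside the exception. This stands: the missing PD cut matters mainly for subjects treated under 5.5.1.

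**The outcome is not certain.** The Protocol speaks of a medical procedure and does not name resection, and the lesion may not be a target lesion. A site could record a treated lesion as not evaluable. This also stands, and it makes the bias conditional. It does not remove the gap, because the result then depends on how each site codes the lesion.

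**The consequence is limited.** Best change is not a listed secondary endpoint, nothing is tested, and no decision rule uses it. Listing 2.6.2 shows target lesions, and procedures are recorded in the eCRF (Protocol 7.4), so an affected subject could be traced. That is right, but a reader of the plot would see no sign of it.

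**Redaction.** SAP 7.3.1.3 to 7.3.1.5 are blacked out and could hold local-treatment rules for other endpoints. Section 7.3.1.6 is readable and refers to none.

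**A stronger reading.** A reader might infer that the 0 mm rule also inflates ORR, or could turn a stop into a continue at the TG E1 futility look. The documents do not support this. The 0 mm rule is limited to the best-change analysis. Best overall response and ORR use the response status that the investigator records under RECIST v1.1, cut at first PD, and the futility look uses investigator assessments too (SAP 10.1). Final tables also pool Parts 1 and 2 by tumor type, and TG E with E1 (SAP 5.2), so shifts worked out on single cohorts would not describe them.

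**Conclusion.** The point holds for best change in target lesion size and its waterfall plot, and for nothing else. As written, SAP 7.3.1.6 can display the effect of permitted local treatment as lesion shrinkage on study drug, and any error is in the favourable direction. It requires that the treated lesion is a target lesion, that the site does not record it as not evaluable, and that scans follow the treatment.

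For an affected subject the distortion can be large: −20% to −100% where the true value is 0%, under the equal-lesion assumption with 1 to 5 target lesions. How many subjects would be affected cannot be derived from the documents, and the 5.5.1 conditions suggest few. The displays are descriptive, so the harm is a misleading bar on a plot and a shifted summary. No claim is made about ORR or TG E1 futility.

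**What to change.** In SAP 7.3.1.6, add a rule to this effect:

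> Best percentage change uses only assessments up to and including the first PD and before any local procedure or radiation to a target lesion. From the date of such treatment the sum of target lesions is not evaluable. Subjects with local treatment of a target lesion are flagged on the waterfall plot.

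Both cuts are needed. The first aligns the window with SAP 7.3.1.2. The second covers a subject treated locally with no PD recorded. SAP 7.3.1.2 needs no edit for this point, and Protocol 5.5.1 is untouched.

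The cost is a few evaluable timepoints. Any real later shrinkage in that subject's untreated lesions is lost too, and a subject treated before the first postbaseline scan would have no value. The recorded procedure must also be matched to the target lesion. Protocol 7.4 has procedures recorded in the eCRF, but no document shows that the form identifies the lesion, so the match may need a manual check.

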### **7.3.2. Acute Myeloid Leukemia**

#### **7.3.2.1. Response Assessment**

Disease assessment for subjects with AML will be performed following the IWG Response Criteria for AML ([Cheson et al 2003](#)). The investigator's assessment will be used to determine responses and will be logged on the eCRF. The schedule for disease assessment will be at screening, every 4 weeks during the study treatment, at the EOT visit, and every 8 to 9 weeks during the disease status follow-up.

Response status per investigator's assessment for AML will be recorded in terms of 3 aspects: (1) altering the natural history of the disease, (2) cytogenetic response, and (3) molecular response. For altering the natural history of the disease, response status will be recorded at each response assessment as CR, CRi, MLFS, PR, peripheral blood blast response, SD, PD, relapse, or treatment failure. For cytogenetic response, response status will be recorded at each response assessment visit as CCyR, no response, not assessed, or NA (ie, normal karyotype). For molecular response, response status will be recorded at each response assessment visit as CMR, no response, not assessed, or NA (ie, no molecular abnormality identified). Refer to Appendix D in the Protocol for the summarized description of the IWG Response Criteria for AML.

### **7.3.2.2. Best Overall Response and Objective Response Rate**

#### **7.3.2.2.1. Altering the Natural History of the Disease**

For AML, BOR based on altering the natural history of the disease is the best response recorded before and including the first progression, which consists of treatment failure, relapse, and PD, in the order of CR, CRI, MLFS, PR, peripheral blood blast response, SD, and progression. In the case of SD, measurements must meet the SD criterion at least once on or after Day 24.

A subject is considered a responder if the subject has a BOR of CR or CRI.

Objective response rate is defined as the proportion of responders based on altering the natural history of the disease. Subjects who do not have sufficient baseline or on-study response assessment information to be adequately assessed for response status will be included in the denominators in the calculations of ORR.

Best overall response will be summarized descriptively. Objective response rate will be estimated with its 95% CI. Confidence intervals will be calculated based on the exact method for binomial distributions.

#### **7.3.2.2.2. Cytogenetic Response**

[figure not shown]
Cytogenetic response is applicable for subjects with abnormal karyotype at baseline. Best overall response for cytogenetic response is the best response recorded before and including the time when the first progression based on altering the natural history of the disease occurs, in the order of CCyR, no response, and not assessed.

[figure not shown]
Best overall response will be summarized descriptively for subjects with abnormal karyotype at baseline.

#### **7.3.2.2.3. Molecular Response**

Molecular response is applicable for subjects with molecular abnormality at baseline. Best overall response for molecular response is the best response recorded before and including the time when the first progression based on altering the natural history of the disease occurs, in the order of CMR, no response, and not assessed.

Best overall response will be summarized descriptively for subjects with molecular abnormality at baseline.

### **7.3.3. Myelodysplastic Syndrome**

#### **7.3.3.1. Response Assessment**

Disease assessment for MDS subjects will be performed following the IWG Response Criteria for MDS ([Cheson et al 2006](#)). The investigator's assessment will be used to determine responses and will be logged on the eCRF. The schedule for disease assessment will be at screening, every 4 weeks during the study treatment, at the EOT visit, and every 8 to 9 weeks during the disease status follow-up.

Response status per investigator's assessment for MDS will be recorded in terms of 3 aspects: (1) altering the natural history of the disease, (2) cytogenetic response, and (3) hematologic improvement. For altering the natural history of the disease, response status will be recorded at each response assessment visit as CR, PR, marrow CR, SD, PD, treatment failure, disease transformation, or relapse after CR or PR. For cytogenetic response, response status will be recorded at each response assessment visit as CCyR, PCyR, or NA. For hematologic improvement, response status will be recorded at each response assessment visit as HI-E, HI-P, HI-N, progression or relapse after hematologic improvement, or NA. Refer to Appendix F in the Protocol for the summarized description of the IWG Response Criteria for MDS.

### 7.3.3.2. Best Overall Response and Objective Response Rate

#### 7.3.3.2.1. Altering the Natural History of the Disease

For MDS, BOR based on altering the natural history of the disease is the best response recorded before and including the first progression, which consists of treatment failure, PD, disease transformation, and relapse after CR or PR, in the order of CR, PR, marrow CR, SD, and progression. In the case of SD, measurements must meet the SD criterion at least once on or after Day 24. When analysis requires the confirmation of CR, PR, or marrow CR, responses must be at least 4 weeks in duration and the rule in [Table 3](#) should be applied.

**Table 3: Confirmation of Complete Remission, Partial Remission, and Marrow Complete Remission for Myelodysplastic Syndrome**

First Assessment	Subsequent Assessment at 4 or More Weeks Later	Confirmed Response
CR	CR	CR
PR	PR or CR	PR
Marrow CR	Marrow CR, PR, or CR	Marrow CR

A subject is considered a responder if the subject has a best overall response of CR.

Objective response rate for MDS is defined as the proportion of responders based on altering the natural history of the disease. Subjects who do not have sufficient baseline or on-study response assessment information to be adequately assessed for response status will be included in the denominators in the calculations of ORR.

Non-confirmed BOR will be summarized descriptively, and the ORR will be estimated with its 95% CI. Best confirmed response of CR, PR, and marrow CR will be summarized descriptively. The confirmed ORR will be estimated with its 95% CI. Confidence intervals will be calculated based on the exact method for binomial distributions.

[figure not shown]

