## APPENDIX F. INTERNATIONAL WORKING GROUP RESPONSE CRITERIA FOR MYELODYSPLASTIC SYNDROME

Category	Response Criteria (Responses Must Be at Least 4 Weeks in Duration)
Complete remission (CR)	Bone marrow: $\leq 5\%$ myeloblasts with normal maturation of all cell lines Persistent dysplasia will be noted Peripheral blood: Hemoglobin (Hgb) $\geq 11$ g/dL, Platelets $\geq 100 \times 10^9/L$ , Neutrophils $\geq 1.0 \times 10^9/L$ Blasts 0%
Partial remission (PR)	All CR criteria if abnormal before treatment, except: Bone marrow blasts decreased by $\geq 50\%$ over pretreatment but still $> 5\%$ Cellularity and morphology not relevant
Marrow CR	Bone marrow: $\leq 5\%$ myeloblasts and decrease by $\geq 50\%$ over pretreatment Peripheral blood: if HI responses, they will be noted in addition to marrow CR
Stable disease (SD)	Failure to achieve at least PR, but no evidence of progression for $> 8$ weeks
Treatment failure	Death during treatment Disease progression characterized by worsening of cytopenias, increase in % of bone marrow blasts, or progression to a more advanced MDS FAB subtype than pretreatment
Disease progression (PD)	For patients with: 
 
- Less than 5% blasts: <math>\geq 50\%</math> increase in blasts to <math>> 5\%</math> blasts
 
- 5%-10% blasts: <math>\geq 50\%</math> increase in blasts to <math>> 10\%</math> blasts
 
- 10%-20% blasts: <math>\geq 50\%</math> increase in blasts to <math>> 20\%</math> blasts
 
- 20%-30% blasts: <math>\geq 50\%</math> increase in blasts to <math>> 30\%</math> blasts
 
 Any of the following: 
 
- At least 50% decrement from maximum remission/response levels in granulocytes or platelets
 
- Reduction in Hgb concentration by <math>\geq 2</math> g/dL
 
- Transfusion dependence
 

Disease transformation	Transformation to AML (30% or more blasts)
Relapse after CR or PR	At least 1 of the following: 
 
- Return to pretreatment bone marrow blast %
 
- Decrement of <math>\geq 50\%</math> from maximum remission/response levels in granulocytes or platelets
 
- Reduction in Hgb concentration by <math>\geq 1.5</math> g/dL or transfusion dependence
 

CYTOGENETIC RESPONSE	
Complete	Disappearance of the chromosomal abnormality without appearance of new ones
Partial	At least 50% reduction of the chromosomal abnormality

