#### 4.1.2. Study Day

If a visit/reporting date is on or after Day 1, then the study day at the visit/reporting date will be calculated as

$$\text{Day \#} = (\text{visit/reporting date} - \text{Day 1 date} + 1).$$

If the visit/reporting date is before Day 1, then the study day at the visit/reporting date will be calculated as

$$\text{Day \#} = (\text{visit/reporting date} - \text{Day 1 date}).$$

A study day of -1 indicates 1 day before Day 1.

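### The SAP accepts MDS stable disease from one record on or after Day 24, but the criteria it cites require more than 8 weeks without progression, so the SD row of the best-response table can be overstated

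*SAP*

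**What the plan says.** SAP 7.3.3.2.1 builds MDS best overall response from the investigator's record at each visit, taking the best one up to and including first progression, "in the order of CR, PR, marrow CR, SD, and progression". Its only timing rule for stable disease is "In the case of SD, measurements must meet the SD criterion at least once on or after Day 24".

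SAP 7.3.3.1 says MDS assessment follows the IWG criteria and adds: "Refer to Appendix F in the Protocol for the summarized description of the IWG Response Criteria for MDS". Appendix F defines stable disease as "Failure to achieve at least PR, but no evidence of progression for $> 8$ weeks".

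Two further parts of SAP 7.3.3.1 bear on the point. The timetable is "The schedule for disease assessment will be at screening, every 4 weeks during the study treatment, at the EOT visit". The categories that can be recorded at a visit are "CR, PR, marrow CR, SD, PD, treatment failure, disease transformation, or relapse after CR or PR". SAP 11.1, which is the place to record changes to protocol-defined analyses, is marked not applicable.

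**The concern.** The two documents set different minimum durations for the same category, and the SAP neither reconciles them nor says that it departs from the criteria. The Day 24 sentence also appears in the AML rule (SAP 7.3.2.2.1). Nothing in Protocol Appendix D contradicts it there, because that appendix has no stable-disease category. The conflict is therefore specific to MDS. In the same MDS section, the SAP does apply Appendix F's 4-week minimum duration to confirmed CR, PR and marrow CR (SAP Table 3), so duration is respected for responses but not for SD.

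What is at stake is how SAP Table 2.2.1 is read for MDS. A reader will take SD there as SD under the cited criteria, when it may rest on a single visit at Week 4. The error can run only one way: subjects who belong under progression, or who cannot be classified, are counted as stable.

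**Working it through.** The plan gives no figure that depends on this rule, so there is nothing to reproduce first. The check is date arithmetic, followed by an illustration of size.

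**Dates.** SAP 4.1.2 sets study day = date − Day 1 date + 1 for dates on or after Day 1.

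- Day 24 is 24 − 1 = 23 elapsed days, and 23/7 = 3.3 weeks.
- Eight weeks is 56 elapsed days, which is Day 57. More than 8 weeks from Day 1 therefore starts at Day 58.
- The gap between the two minimums is 58 − 24 = 34 days.
- Four-weekly visits fall nominally on Days 29, 57 and 85. With the ±2-day window in Protocol Table 7, the Week 4 visit falls on Days 27 to 31 and the Week 8 visit on Days 55 to 59.
- Every Week 4 visit thus passes the Day 24 test, and none can show more than 8 weeks without progression. A Week 8 visit on its nominal day is exactly 8 weeks and also falls short.

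**Worked case.** A subject has SD recorded on Day 29 and progression on Day 57. Under the SAP, the SD record is on or after Day 24 and SD ranks above progression, so best response is SD. Under Appendix F, progression came at 8 weeks, not after more than 8 weeks, so SD is not met.

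**What else moves.** An MDS responder is CR only (SAP 7.3.3.2.1). The confirmed summaries cover CR, PR and marrow CR. MDS futility in TG D1 counts CR or marrow CR (Protocol 9.6). SD enters none of these, so the change in each is 0.

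**Size.** The documents give no MDS progression rate. Assume that time to progression among non-responders is exponential with median m weeks: S(t) = 2^(−t/m). The affected subjects are stable at Week 4 and progress by Week 8.

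- Share of all non-responders: S(4) − S(8).
- Share of those still stable at Week 4: 1 − S(8)/S(4) = 1 − 2^(−4/m).

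| m (weeks) | S(4) | S(8) | Share of non-responders | Per 15 non-responders | Share of those stable at Week 4 |
|---|---|---|---|---|---|
| 6 | 0.630 | 0.397 | 23% | 3.5 | 37% |
| 8 | 0.707 | 0.500 | 21% | 3.1 | 29% |
| 12 | 0.794 | 0.630 | 16% | 2.5 | 21% |
| 16 | 0.841 | 0.707 | 13% | 2.0 | 16% |
| 26 | 0.899 | 0.808 | 9% | 1.4 | 10% |

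The 15 is only a convenient base, because the documents do not state how many MDS subjects are expected. The table leaves out subjects with SD at Week 4 and no later assessment. The SAP also calls them SD, although the criteria cannot be shown to be met.

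**The case against.** The best textual defence is that meeting the SD criterion already imports the 8 weeks from Appendix F, so that Day 24 is only an added floor. On that reading Day 24 does no work. The visit categories also contain no not-evaluable or too-early option, so a non-progressing non-responder at Week 4 can only be recorded as SD. A programmer following the text would count that record. The reading shows some ambiguity but does not remove the conflict.

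On importance, the other side is largely right. The study is exploratory with no formal tests (Protocol 9.3), the SAP has no efficacy hypotheses (7.2), and best response is only described. Small tumour-type tables may become listings (SAP 5.2), and the planned by-visit response listing (2.6.1) would show early SD followed by progression. The rule that lets TG A1 subjects switch to a combination has its own 3-month threshold (Protocol 4.1.2) and does not use this category.

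The size is also uncertain. The model is assumed, and progression must be detected by Week 8. Marrow assessment in Cycle 2 is only encouraged, with the response marrow due at Cycle 4 Day 1 or earlier if clinically indicated (Protocol 7.6).

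A reader might infer that the plan overstates MDS efficacy in general, or the response rate in particular. The documents do not support that, because SD counts as a response in no MDS rule.

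**Conclusion.** The plan is wrong as written, within narrow limits. Following SAP 7.3.3.2.1 puts subjects with SD at Week 4 and progression at Week 8 in a row that the cited criteria do not allow. Only the split between SD and progression or not evaluable in the descriptive, unconfirmed MDS best-response table can move, together with any SD-or-better total taken from it. Whether it moves depends on such subjects occurring.

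If progression is exponential and is detected at Week 8, about 9% to 21% of non-responders would be affected for medians from 26 down to 8 weeks. The higher figures of 21% and 29% (medians of 12 and 8 weeks) apply only to those still stable at Week 4 and should not be read as shares of the whole table. The date mismatch itself needs no assumption beyond counting the 8 weeks from Day 1, a starting point that Appendix F does not state.

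**What to change.** In SAP 7.3.3.2.1, replace the Day 24 sentence for MDS with a rule that covers four things:

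1. **Minimum.** SD requires no progression for more than 8 weeks counted from Day 1, that is, Day 58 or later by the SAP 4.1.2 formula.
2. **Week 8 visits.** State whether a visit within the window (Days 55 to 59) that shows no progression satisfies the minimum, or whether the next assessment decides. A bare cut-off at Day 57 would admit exactly 8 weeks. A bare cut-off at Day 58 would reject visits made on time or slightly early. The convention should therefore be written down.
3. **Earlier progression.** Subjects without a better response who progress before the minimum have a best response of progression.
4. **No later assessment.** Add a not-evaluable category for these subjects. The MDS ordering has none at present, whereas the solid-tumour rule (SAP 7.3.1.2) does provide a fallback.

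The cost is a short SAP edit and a small programming change, with no new data collection. Some subjects will move from SD to progression or not evaluable. If the sponsor prefers to keep Day 24, the lesser alternative is to record it in SAP 11.1 as a departure from Appendix F and label the table row accordingly.
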